## List of abbreviations

BMI	Body mass index
BP	Blood pressure
CRF	Case record form
CBC	Complete blood count
CI	Confidence interval
CK	Creatine kinase
FDA	Food and Drug Administration
FSH	Follicle stimulating hormone
GCP	Good Clinical Practice
ICH	International Conference on Harmonization
ICSI	Intracytoplasmic sperm injection
IND	Investigational New Drug Application
IRB	Institutional Review Board
LC/MS	Liquid chromatography/mass spectroscopy
LH	Luteinizing hormone
MedDRA	Medical Dictionary for Regulatory Activities
NICHD	National Institute of Child Health and Human Development
OAT	Oligoasthenoteratozoospermia
PSA	Prostate Specific Antigen
SAE	Serious adverse event
T	Testosterone
TESE	Testicular sperm extraction

## Synopsis

Study Title	A pilot trial of 13- cis retinoic acid for the treatment of men with azoospermia
Study Phase	II
Sponsor	National Institute of Child Health and Human Development
Study Drug	13- cis retinoic acid
Objective	
Primary Objective: To determine the effect of 13-cis retinoic acid administration on the appearance of sperm in the ejaculate among men presenting with azoospermia
 
Approach: Twenty men with infertility, aged 21-60, due to azoospermia (no apparent sperm in the ejaculate on two separate occasions) will be enrolled in a single-arm pilot trial of daily oral therapy of 20 mg twice daily of 13-cis retinoic acid for 32 weeks. The impact of treatment on the appearance of sperm in the ejaculate will be determined by monthly semen analyses.
 
Secondary Objectives:
 
 
• To determine the side effects associated with treatment with 13-cis retinoic acid
 

PI	[name] MD, MPH
Rationale	Men with infertility from azoospermia and normal gonadotropins have few options for treatment. Recent research has demonstrated that lower intratesticular concentrations of 13- cis retinoic acid are associated with abnormal sperm production. Older studies of 13- cis retinoic acid administration to normal men demonstrated increases in sperm concentrations. Our recent pilot study in men with oligoasthenozoospermia demonstrated increased sperm production in roughly ½ of men with treatment, including several who started with sperm counts very close to zero. However, the effect of 13- cis retinoic acid on sperm concentrations in men with azoospermia has never been studied. If 13- cis retinoic acid allowed men with azoospermia to produce ejaculated sperm, it could help men with azoospermia father pregnancies using ICSI without the need for testicular biopsy or testicular sperm extraction (TESE).

Study Design	
We will conduct an unblinded, pilot study to determine the impact of therapy with 13-cis retinoic acid on sperm indices in azoospermic men. Twenty azoospermic men, ages 21-60 will be enrolled in a 32-week study of 20 mg twice daily of 13-cis retinoic acid. The subjects will be closely followed for side effects related to treatment. The impact of treatment on the appearance of sperm in the ejaculate will be determined by monthly seminal fluid analyses.
 
All aspects of this study will be performed in compliance with Good Clinical Practice (GCP) regulations, ICH guidelines, the Declaration of Helsinki, and under an FDA Investigational New Drug (IND) application.

Number of Subjects	Twenty men.
Duration of Trial	Enrollment should be completed in about 18 months, resulting in total study duration of about 36 months including screening, treatment phase, end of study visit procedures, close out and data analysis.
Duration of Treatment	The active treatment phase will be 32 weeks.
Dosage and Regimen	13- cis retinoic acid at 20 mg twice daily with meals for 32 weeks.
Inclusion Criteria	Subjects will be infertile men with azoospermia on at least two semen analyses separated by at least one week and no pregnancy with partner with normal cycles and normal hysterosalpingogram despite >1 year of unprotected intercourse.
Exclusion Criteria	Exclusion criteria include: hypogonadotropic hypogonadism (that might respond to gonadotropin injections), the use of anabolic steroids, illicit drugs, or the consumption of more than 4 alcoholic beverages daily, severe mental health problems, or current therapy with retinoic acid (e.g. Accutane) or vitamin A.
Efficacy Parameters	The appearance of sperm in the ejaculate during treatment
Safety Parameters	
 
• CBC, clinical chemistry panel (glucose, liver and renal function tests including urea, creatinine, albumin, calcium alanine aminotransferase, aspartate aminotransferase, alkaline phosphatase, bilirubin), CK, full lipid panel
 

	
including: Total cholesterol, HDL, LDL and fasting triglycerides at baseline, week 8, 16, 24 and 32 of treatment, and study exit. Additional measures will be conducted if any abnormal values are found until the end of study visit.
 
 
• Adverse event and concomitant medications throughout the study. Other safety parameters include vital signs; and changes in pre- and post-treatment physical examination results and score on the PHQ9 depression questionnaire.
 

Evaluations	
The following determinations will be made in all subjects:
 
 
• Semen analysis will be collected twice during screening and every four weeks during treatment and twice during recovery
 
• Serum samples will be collected for the measurement of: vitamin A, all-trans and 13-cis retinoic acid, testosterone, FSH and LH. Serum for these measures will be collected before the beginning of the treatment, and every two months during treatment and sy study exit.
 

Other Assessments	
Demographic characteristics, including age and race, will be collected.

Statistical Analysis	
The primary endpoint is the appearance of sperm in the ejaculate of treated men between baseline and 32 weeks. This analysis will be conducted using a Wilcoxon signed-rank test.

## 1.0 Introduction and Background

Infertility affects 10-15% of all couples, with 1.5 million couples seeking medical assistance for infertility yearly (1). Infertility attributable to the male partner accounts for 30-40% of all cases of infertility. The most common form of male infertility involves some type of impairment in spermatogenesis (2). Unfortunately, over 80% of men with infertility from impaired spermatogenesis do not have a medically treatable cause, such as a gonadotropin deficiency (3). In men with idiopathic infertility, surgical sperm extraction from the testes coupled with *in vitro* fertilization or intra-cytoplasmic sperm injection offers some hope of fertility; however, these procedures are invasive, expensive, unsuccessful in 30-40% of cases, and don't address the underlying cause of infertility (4). Therefore, new approaches to the treatment of male infertility are sorely needed.

The essential role of vitamin A (retinol) in spermatogenesis has been long appreciated. Vitamin A deficient male mice are sterile due to impaired spermatogenesis and supplementation of deficient mice with vitamin A restores fertility (5, 6). Vitamin A is required for spermatogenesis as it is converted to retinoic acid in the seminiferous tubules via the activity of testes-specific retinol and retinal dehydrogenases. Retinoic acid is known to mediate most of the effects of vitamin A in tissues. In the testes, two retinoic acid receptors,  $\alpha$  and  $\gamma$ , are present in both Sertoli cells and developing germ cells (7-10), and targeted deletion of these receptors in mice results in male infertility (11-13). From this work, it is clear that retinoic acid plays several essential roles in spermatogenesis, including necessary functions in spermatogonial differentiation, spermatid adhesion to Sertoli cells and spermiation (14). Given the crucial role of retinoic acid in spermatogenesis, it seems quite possible that some men with "idiopathic" infertility have intratesticular concentrations of retinoic acid below those necessary to initiate and/or maintain optimal spermatogenesis. In theory, poor dietary intake of vitamin A could lead to infertility; however, a nutritional cause of infertility seems improbable in the U.S.

More likely, low intratesticular concentrations of retinoic acid could occur in infertile men either due to impaired retinoic acid biosynthesis from vitamin A or increased metabolism of retinoic acid to inactive metabolites within the testes.

Despite the known importance of retinoic acid for spermatogenesis in animals, there has been relatively little work examining the role of retinoic acid on spermatogenesis in humans. Intriguingly, there is a suggestion that the administration of retinoic acid to men may improve sperm production. During the development of 13-cis retinoic acid (Accutane) for acne, three human studies examining the effect of oral administration of 13-cis-retinoic acid on sperm production in men were performed to determine if 13-cis retinoic acid was harmful to male fertility. Interestingly, men in these studies had increased sperm concentrations during treatment (see below), suggesting that 13-cis retinoic acid administration enhanced spermatogenesis in these normal men with acne (15-17). We recently completed a pilot study in 20 men with infertility from oligoasthenoteratozoospermia. In this study, roughly ½ of the men experienced significant improvements in their sperm production, suggesting this treatment is useful for men with oligoasthenoteratozoospermia. In this proposal, we will perform a clinical trial of retinoic acid administration to infertility patients with azoospermia to determine whether retinoic acid therapy can initiate sperm production in men with azoospermia. If the administration of retinoic acid were shown to improve spermatogenesis in some infertile men with azoospermia, it would have tremendous significance for our current approach to the treatment of men with infertility who could avoid the need for testicular biopsy and/or testicular sperm extraction. Because of its widespread use in humans for over 25 years, 13-cis retinoic acid is widely available in a generic formulation and could be quickly incorporated into male infertility treatment algorithms. Ideally, retinoic acid therapy would allow a man to make sufficient sperm for ICSI, dramatically increasing his chances of fathering a pregnancy.

## **Objectives**

### **2.1 Primary Objective:**

To determine the effect of 13-*cis* retinoic acid administration on the appearance of sperm in the ejaculation in men with azoospermia.

### **2.2 Secondary Objectives:**

- To determine the side effects and tolerability of treatment with 13-*cis* retinoic acid in men with azoospermia

### **3. Rationale, Benefits and Risks**

Male infertility is common and difficult to treat unless men have an easily identified gonadotropin deficiency. Many men have idiopathic infertility. We have shown that men with abnormal spermatogenesis have lower than normal levels of intratesticular retinoic acid, suggesting that intratesticular retinoic acid deficiency is associated with infertility, and have performed a pilot study in men with idiopathic oligoasthenoazoospermia demonstrating that half of these men increase their sperm production on treatment. In this study, we aim to determine if retinoic acid therapy can convert men with azoospermia into men with oligozoospermia. The medication, 13-*cis* retinoic acid, is widely available and prescribed for the treatment of acne, suggesting that serious adverse events are unlikely, especially at the low doses to be tested.

### **4. Compliance**

All aspects of this study will be performed according to Good Clinical Practice GCP regulations, the Declaration of Helsinki and ICH guidelines, under an active FDA Investigational New Drug (IND) (#120703).

## **5. Study Design**

We will conduct an open-label pilot trial to determine the impact of therapy with 13-*cis* retinoic acid on sperm indices in infertile men. Twenty infertile men with azoospermia will be enrolled in a 32-week study of 20 mg twice daily of 13-*cis* retinoic acid. The subjects will be closely followed for side effects related to treatment. The impact of treatment on indices of spermatogenesis will be determined by monthly seminal fluid analyses.

## **6. Duration of the Study**

*Subjects:* Subjects will undergo a screening phase of up to 60 days. The first 20 subjects meeting the enrollment criteria will be enrolled. The treatment phase will last for 32 weeks and subjects will have two post-treatment visits, about 12 and 24 weeks after the end of treatment.

Enrollment should be completed in approximately 18 months, resulting in total study duration of about 36 months including screening, treatment phase, end of study visit procedures, close out and data analysis.

## **7. Number of Subjects**

20 men will participate in the study. We may need to screen up to 50 men to find 20 men eligible to participate.

## **8. Dosage and Administration**

13-*cis* retinoic acid at 20 mg twice daily (purchased commercially) with meals

## **9. Selection of Subjects**

### **9.1.1 Inclusion Criteria**

1. Subjects will be infertile men (no pregnancy with partner with normal cycles and normal hysterosalpingogram despite >1 year of unprotected intercourse).
2. Azoospermia (no sperm apparent in centrifuged semen) as assessed by semen analysis on two occasions separated by one week.
3. In the opinion of the investigator, is able to comply with the protocol, understand and sign an informed consent and HIPAA form.

### **9.2 Exclusion Criteria**

Men who meet any of the following criteria are NOT eligible for enrollment in the trial:

1. Men participating in another clinical trial
2. Men not living in the catchment area of the clinic
3. Clinically significant abnormal findings at screening
4. Hypogonadotropic hypogonadism (that might respond to gonadotropin injections),
5. The use of anabolic steroids, illicit drugs, or the consumption of more than 4 alcoholic beverages daily
6. Severe mental health problems requiring medications
7. Current therapy with retinoic acid (e.g. Accutane) or vitamin A
8. Score of greater than 15 on the PHQ9 (mood) questionnaire
9. Abnormal serum chemistry values according to local laboratory normal values which indicate liver or kidney dysfunction. Other abnormal lab values may also be exclusionary, at the discretion of the investigator
10. Men with a personal history of serious psychiatric disorders
11. Men currently receiving tetracycline containing medications
12. Men currently receiving phenytoin
13. Men with a history of inflammatory bowel disease
14. Men with a history of bone disease
15. Men who have used isotretinoin within eight weeks of the start of dosing
16. Men with elevated serum triglycerides

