### 12.4.1 Visit 1 (week 0)

This is the day 1 of treatment. The following will be done at this visit:

- Vital signs (pulse, blood pressure) and weight will be taken and recorded.
- Subjects will be questioned regarding concomitant medications and adverse events. If the subject is taking a medication that is listed as disallowed the subject should not be enrolled in the study.
- The subject will complete the PHQ9 questionnaire (see appendix 5)
- Subjects will be given enough supply of study medication for 30 days. This doesn't allow enough medication, in case subject has to come in at week 4 + 6 days.

- A study drug log will be dispensed to record the date and time of administration of the study drug. Subjects will be instructed to take the study drug twice a day, except on the day of the visit. Subjects will be scheduled to return to the clinic after 28 +/- 6 days.

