#### **12.4.2 Visits 2-9 (Treatment Visits)(+/- 6 days)**

These visits are for weeks 4, 8, 12, 16, 20, 24, 28 and 32. The following procedures will be done at these visits:

- Vital signs (pulse, blood pressure) and weight will be taken and recorded.
- The subject will complete the PHQ9 mood questionnaire
- Complete physical exam including and testicular examination and volume measurement will be performed.
- Subjects will be questioned regarding concomitant medications and adverse events.
- Any unused study drug counted for drug accountability and returned to subject? At treatment visit 32 or early exit visit, all unused study drug will be collected.
- Study drug log will be reviewed to check the date and time of drug administration. These logs will be collected at each treatment visit.
- A blood sample will be drawn at week 8, 16, 24 and 32. The time of day of the blood draws will be recorded in the source document.
- A semen sample will be obtained for the presence of sperm, and, if present, the measurement of sperm count, concentration, motility and morphology
- Fasting blood samples will be obtained for the following measurements: CBC, clinical chemistry including glucose, liver and renal function tests (urea, creatinine, albumin, calcium, alanine aminotransferase, aspartate aminotransferase, gamma glutamine transferase, alkaline phosphatase, bilirubin, and albumin), creatine kinase, full lipid panel including total cholesterol, HDL and LDL, triglycerides, hematology (hematocrit, hemoglobin), and testosterone, FSH and LH at weeks 8, 16, 24, and 32.
- In addition, blood samples will be collected at each visit for two serum samples to be frozen for the future analysis of serum retinoid levels.
- Subjects will be scheduled to return to the clinic for follow-up visits.
- Subjects will be given the next month's supply of study drug at visits 2-8 (weeks 4, 8, 12, 16, 20, 24 and 28).

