### **12.4.3 Visit 10 and 11 (Follow-up Visits) +/- 6 days**

These visits are for weeks 44 and 56. The following will be done at these visits:

- Vital signs (pulse, blood pressure and respiratory rate) will be taken and recorded.
- The subject will complete the mood (PHQ-9) questionnaire.
- Subjects will be questioned regarding concomitant medications and adverse events.
- Fasting blood samples (week 56 only) will be obtained for the following measurements: CBC, clinical chemistry including glucose, liver and renal function tests (urea, creatinine, albumin, calcium, alanine aminotransferase, aspartate aminotransferase, gamma glutamine transferase, alkaline phosphatase, bilirubin, and albumin), creatine kinase, full lipid panel including total cholesterol, HDL and LDL, triglycerides, hematology (hematocrit, hemoglobin), and testosterone, FSH and LH. In addition, two serum samples will be frozen for the future analysis of serum retinoid levels.
- A semen sample will be obtained to ascertain the presence of sperm, and, if present, the measurement of sperm count, concentration, motility and morphology

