#### **Post-Admission Withdrawal Criteria**

Subjects may be discontinued prematurely for any of the following reasons:

- Emergence of a severe condition(s) such that, in the judgment of the investigator, continuation in the trial would negatively impact the health of the subject.
- Personal reasons (*e.g.* withdrawn consent).
- Non-compliance with study drug

- Subject lost to follow-up
- A severe skin reaction judged by the investigator to potentially be related to the study drug
- A persistent elevation of serum triglycerides
- Onset of neutropenia
- New onset of hearing disorder
- New onset of visual changes
- Onset of abdominal pain, rectal bleeding or severe diarrhea
- Persistent, significant increase of liver enzymes or bilirubin
- New onset of significant serum glucose elevation
- New onset of headache associated with nausea and vomiting
- Persistent elevation of serum calcium
- Development of kidney stones
- Increase in the PHQ9 score to >15 (suggestive of moderately severe depression)

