Appendix 2: PHQ9 Questionnaire

**PATIENT HEALTH QUESTIONNAIRE (PHQ-9)**

NAME: \_\_\_\_\_ DATE: \_\_\_\_\_

Over the last 2 weeks, how often have you been bothered by any of the following problems?  
(use "✓" to indicate your answer)

	Not at all	Several days	More than half the days	Nearly every day
1. Little interest or pleasure in doing things	0	1	2	3
2. Feeling down, depressed, or hopeless	0	1	2	3
3. Trouble falling or staying asleep, or sleeping too much	0	1	2	3
4. Feeling tired or having little energy	0	1	2	3
5. Poor appetite or overeating	0	1	2	3
6. Feeling bad about yourself—or that you are a failure or have let yourself or your family down	0	1	2	3
7. Trouble concentrating on things, such as reading the newspaper or watching television	0	1	2	3
8. Moving or speaking so slowly that other people could have noticed. Or the opposite—being so fidgety or restless that you have been moving around a lot more than usual	0	1	2	3
9. Thoughts that you would be better off dead, or of hurting yourself	0	1	2	3

add columns  +  +

(Healthcare professional: For interpretation of TOTAL, TOTAL:   
please refer to accompanying scoring card).

10. If you checked off any problems , how difficult have these problems made it for you to do your work, take care of things at home, or get along with other people?	Not difficult at all	_____
	Somewhat difficult	_____
	Very difficult	_____
	Extremely difficult	_____

Copyright © 1999 Pfizer Inc. All rights reserved. Reproduced with permission. PRIME-MD® is a trademark of Pfizer Inc. A2663B 10-04-2005

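### Both PHQ9 rules use only a total above 15, so a positive self-harm answer can meet neither, and no same-day check of that item is written.

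*Combined protocol and SAP*

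**What the plan says.** The protocol contains two decision rules that use the PHQ9.

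- **Entry.** Section 9.2, item 8, excludes a man with a "Score of greater than 15 on the PHQ9 (mood) questionnaire".
- **On treatment.** The withdrawal criteria in section 13 include "Increase in the PHQ9 score to >15 (suggestive of moderately severe depression". The list is introduced permissively: a man who meets an item may be stopped, not must be.

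The form in Appendix 2 has nine items scored 0 to 3. Item 9 reads "Thoughts that you would be better off dead, or of hurting yourself". The form's interpretation note concerns the total and refers to a scoring card that is not among the listed appendices.

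The visit text has the form filled in, and says no more about it:

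- Section 12.4.1 (Day 1): "The subject will complete the PHQ9 questionnaire".
- Section 12.4.2 (weeks 4 to 32): "The subject will complete the PHQ9 mood questionnaire". The same section states: "Subjects will be given the next month's supply of study drug at visits 2-8".
- Section 12.4.3 (weeks 44 and 56): "The subject will complete the mood (PHQ-9) questionnaire".

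Appendix 1 also marks a PHQ9 at the first screening visit, but section 12.3.1 does not list it. Among the safety parameters, the Synopsis names the "score on the PHQ9 depression questionnaire" and no single item.

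**The concern.** The protocol treats mood as a specific safety matter. It excludes men on psychiatric history or a high score, repeats the questionnaire throughout, and lists a rise in score as a reason to stop. Yet the one item that asks directly about self-harm has effect only through the total, to which it adds at most 3 points of 27. Under the PHQ9 rules as written, a man who reports such thoughts nearly every day could be enrolled or handed the next month's drug.

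Timing adds to this. Other information has a written review step: laboratory reports go to the investigator (12.2), and drug logs are reviewed at each visit (11.1 and 12.4.2). The PHQ9 has none. A form that nobody reads until the man has gone gives no protection until the next contact. Section 13 also names single symptoms as grounds for stopping, such as new visual changes or a hearing disorder, but not self-harm thoughts.

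What is at stake is participant safety. The primary endpoint and its analysis are not affected.

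**Working it through.** **Inputs.** Nine items scored 0 to 3 (Appendix 2); cut-off above 15 (9.2 item 8 and section 13); visit and dispensing schedule (12.4.1 to 12.4.3); 20 men (section 7); return after Day 1 at 28 ± 6 days (12.4.1). The plan states no figure on this point that needs reproducing.

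**Step 1: the total needed.** The range is 0 to 9 × 3 = 27. Scores are integers, so above 15 means 16 or more.

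**Step 2: what the rules miss.** If item 9 is scored *k*, the other eight items (maximum 8 × 3 = 24) must sum to at least 16 − *k* to meet either rule. They can sum to 15 − *k* without meeting it.

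| Item 9 answer | Others needed to meet the rule | Highest sum of others that misses it |
|---|---|---|
| 1 | 15 | 14 |
| 2 | 14 | 13 |
| 3 | 13 | 12 |

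With item 9 = 3, totals from 3 to 15 miss the rule. Such a man is 16 − 15 = 1 to 16 − 3 = 13 points short.

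Counting every possible set of answers with item 9 = 3, 36,814 of 4⁸ = 65,536 (56%) total 15 or less. This shows only that the gap is not a corner of the scale. It counts possible forms and does not estimate how often patients would give such answers.

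**Step 3: exposure under the visit text.**

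- Forms per man: 1 (Day 1) + 8 (weeks 4 to 32) + 2 (weeks 44 and 56) = 11. With the screening form in Appendix 1 the count is 12.
- Forms at dispensing visits: Day 1 and weeks 4, 8, 12, 16, 20, 24 and 28 = 8 per man, so at most 8 × 20 = 160 if nobody drops out.
- Forms at weeks 32, 44 and 56, when no drug is dispensed: 3 × 20 = 60.

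**Step 4: delay if a form is not read on the day.** From Day 1 to the next visit is 28 − 6 = 22 to 28 + 6 = 34 days. From week 32 to week 44 is nominally 12 weeks.

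**Step 5: search for another trigger.** None of the entry criteria, visit procedures, withdrawal criteria, adverse event section or schedule of events mentions item 9, suicidal thoughts, or a review of the form before the man leaves.

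**The case against.** The strongest reply is that the PHQ9 rules should not be read apart from the rest of the protocol.

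- **At entry.** Exclusion 3 covers clinically significant abnormal findings and is mandatory once met. Exclusions 6 and 10 cover severe mental health problems needing medication and a history of serious psychiatric disorder. Exclusion 8 cannot be applied unless the form is scored before enrolment, so scoring at entry is implied.
- **On treatment.** Adverse events are asked about at every visit, and section 12.4.2 requires a full physical examination at weeks 4 to 32. Section 13 lets the investigator stop a man who develops a severe condition. Because that list is permissive, a total of 16 also leads to action only by judgement.
- **Unseen material.** All men go through iPLEDGE counselling and sign an isotretinoin-specific consent. Those materials and the scoring card are not available here.

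Much of this is fair. A careful investigator could act on a positive item 9 under the existing text, and implied scoring at entry narrows the timing complaint mainly to the treatment and follow-up visits. But each route depends on someone noticing the answer, and nothing requires anyone to look at item 9 before the man leaves. The examination is not linked to the questionnaire. It does suggest that a clinician is already present at those visits, which makes the remedy easier. The permissive wording in section 13 is a further looseness, not a safeguard.

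It is also true that the documents do not dictate the trigger level for item 9. Any answer above 0 is a judgement. It is defensible here because it prompts an assessment, not automatic exclusion.

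**Conclusion.** The concern holds. Both PHQ9 rules act only on a total of 16 or more, and a man with the highest self-harm answer and up to 12 points elsewhere meets neither. No text requires the form to be scored, or item 9 read, before he leaves or is given drug. Up to 160 forms at dispensing visits, and 60 at the later visits, would be completed without that step.

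The scoring conclusion rests only on integer scoring, and the form counts assume that all 20 men attend every visit. The finding is limited to the protocol text: it does not show that men would go unassessed in practice. How often item 9 would be positive with a total of 15 or less cannot be estimated from the documents. The change should be made because it is cheap and the harm it guards against may be irreversible.

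**What to change.** After the PHQ9 line in sections 12.4.1, 12.4.2 and 12.4.3, add:

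> Staff score the PHQ9 and check item 9 before the man leaves and before any drug is dispensed. Any item 9 answer above 0 prompts same-day clinical assessment by the investigator, whatever the total. Study drug is withheld until this is done.

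Apply the same wording to the screening form marked in Appendix 1, if it is used. Cross-reference it in 9.2 item 8 and in the PHQ9 line of section 13, so that the outcome of the assessment is a stated ground for exclusion or discontinuation.

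The cost is protocol wording, a brief check of each form, and investigator time when item 9 is positive. The form and visits are already in place. The investigator must be reachable on each PHQ9 visit day, which the text does not now promise. A few men who would otherwise count toward the 20 might be excluded or stopped.
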